4. ELF
5. NL
6. Spirometry
7. Sputum induction

The subjects will be discharged with contact information for a study physician. They will be scheduled to return for a second session, with a minimum of 2 weeks and a

maximum of 6 weeks between exposures. The sessions will be identical except for the atmosphere in the chamber, which is randomized.

Baseline measurements provide safety information prior to each exposure. Given the level of the O3 and the procedures that subjects are asked to undergo, we do not anticipate any health concerns, but if they do arise, they will be immediate, therefore there are no scheduled visits beyond day 3 of the 2nd session. However, subjects will be encouraged to contact the study coordinator or physician at any time up to a month later if they have any concerns regarding their health or effects from the study.

#### **4.1 Withdrawal Visit**

If a subject withdraws from the study, any safety measures deemed necessary by the covering physician will be performed. This includes physical examination with vital signs, ECG measurement, or spirometry.

#### **4.2 Unscheduled Visit**

If a subject has an unexpected response to any study procedure, any safety measures deemed necessary by the covering physician will be performed. This includes physical examination with vital signs, ECG measurement, or spirometry.

#### **4.3 Laboratory Procedures/Evaluations**

##### **4.3.1 Clinical Laboratory Evaluations**

Blood will be sent to Labcorp, INC, for a complete blood count and chemistry values at screening.

##### **4.3.2 Special Assays or Procedures**

NLF will be collected and processed to obtain a cellular and cell-free fraction as described by us before, which will be analyzed for markers of inflammation and changes in immune responses. Cell-free nasal lavage fluid will be used to assess changes in markers of inflammation, host defense responses, and overall immune status. NLF cells will be used to assess changes in PMN influx as well as gene expression profiles associated with the exposure.

Superficial scrape biopsies will be obtained as described by us before and processed to yield both RNA and DNA. Total RNA will be analyzed for gene expression profiles associated with the exposures, while DNA samples will be used to determine epigenetic changes associated with the exposure.

Epithelial lining fluid (ELF) will be obtained by placing a strip of synthetic absorbent material (SAM) into the nostril, securing it with a nose clip, and removing it after about 2 minutes (you may want to copy language from our TCORS SOP here). ELF strips will be stored at -80oC until elution using PBS+BSA. ELF fluid will be used to assess changes in immune and inflammation mediators.

Sputum will be processed as previously published –in brief: plug material from sputum will be weighted and homogenized with DPBS (8x wt of selected plug material), centrifuged and supernatants recovered for proteomic assessment; sputum will be further homogenized with DTT (0.1%), filtered, centrifuged and the cell pellet recovered. The cell pellet will be re-suspended in an appropriate volume to a desired cell concentration ( $1 \times 10^6$  cells/ml) for cytopsin slide generation; slides will be fixed and stained and read for differential leukocyte analysis. The remaining cells will be resuspended in Trizol reagent for RNA extraction and future mRNA/miRNA analysis using Nanostring technology.

Sputum: MesoScale Discovery to assay fluid phase proteins (cytokines); hemacytometry to assay total cell counts; NanoString technology to assay genes of interest; Flow cytometry: to assay functional cellular endpoints such as phagocytosis, intracellular oxidative burst, cell surface markers

In addition, we will genotype for SNPs of interest such as GSTM1 and other oxidant related genotypes; we will analyze mRNA expression for inflammation, immune and oxidant associated genes.

#### **4.3.3 Reporting of SAEs and AEs to IRB**

AEs and SAEs will be reported per UNC standard reporting procedures.

## **5 ETHICS/PROTECTION OF HUMAN SUBJECTS**

### **5.1 Informed Consent Process**

Informed consent is a process that is initiated prior to the individual agreeing to participate in the study and continues throughout study participation. Extensive discussion of risks and possible benefits of study participation will be provided to subjects and their families, if applicable. A consent form describing in detail the study procedures and risks will be given to the subject. Consent forms will be IRB-approved, and the subject is required to read and review the document or have the document read to him or her. The investigator or designee will explain the research study to the subject and answer any questions that may arise. The subject will sign the informed consent document prior to any study-related assessments or procedures. Subjects will be given the opportunity to discuss the study with their surrogates or think about it prior to agreeing to participate. They may withdraw consent at any time throughout the course of the study. A copy of the signed informed consent document will be given to subjects for their records. The rights and welfare of the subjects will be protected by emphasizing to them that the quality of their clinical care will not be adversely affected if they decline to participate in this study.

The consent process will be documented in the clinical or research record.

### **5.2 Subject Confidentiality**

Subject confidentiality is strictly held in trust by the investigators, study staff, and their agents. This confidentiality is extended to cover testing of biological samples and genetic tests in addition to any study information relating to subjects.

The study protocol, documentation, data, and all other information generated will be held in strict confidence. No information concerning the study or the data will be released to any unauthorized third party, however the subject may request copies of all clinical values, including lab results, ECG and spirometry.

## 6 DATA HANDLING AND RECORD KEEPING

Paper documents will be maintained by the PI or designee. All data will be entered into a REDCap database.

This study will comply with the [NIH Public Access Policy](#), which ensures that the public has access to the published results of NIH funded research. It requires scientists to submit final peer-reviewed journal manuscripts that arise from NIH funds to the digital archive [PubMed Central](#) upon acceptance for publication.

The International Committee of Medical Journal Editors (ICMJE) member journals have adopted a clinical trials registration policy as a condition for publication. The ICMJE defines a clinical trial as any research project that prospectively assigns human subjects to intervention or concurrent comparison or control groups to study the cause-and-effect relationship between a medical intervention and a health outcome. Medical interventions include drugs, surgical procedures, devices, behavioral treatments, process-of-care changes, and the like. Health outcomes include any biomedical or health-related measures obtained in patients or participants, including pharmacokinetic measures and adverse events. The ICMJE policy requires that all clinical trials be registered in a public trials registry such as [ClinicalTrials.gov](#), which is sponsored by the National Library of Medicine. Other biomedical journals are considering adopting similar policies. For interventional clinical trials performed under NIDCR grants and cooperative agreements, it is the grantee's responsibility to register the trial in an acceptable registry, so the research results may be considered for publication in ICMJE member journals. The ICMJE does not review specific studies to determine whether registration is necessary; instead, the committee recommends that researchers who have questions about the need to register err on the side of registration or consult the editorial office of the journal in which they wish to publish.

## 7 DATA ANALYSIS

Aim 1. Characterize ozone induced changes in nasal PMN counts.

This is a randomized, double blind, crossover pilot study, studying the changes in cells of nasal lavage (neutrophilla) after low-level ozone exposure. First, descriptive analysis will be conducted to examine potential ozone exposure effect and period effect. Second, two sample tests such as t-test and Mann Whitney test will be used to compare changes in response in clean air and ozone exposure groups. In general, carry-over effect is first tested. In the absence of significant carry-over effect, pooled data from both periods can be used to estimate the ozone exposure effect. Otherwise, only period 1 data can be used. We will report effect estimates, standard deviation as well as confidence intervals for ozone exposure effect and potential period effect. Finally, a random effects model will be fitted to assess the ozone exposure effect. Confidence intervals will be reported.

Aim 2. Characterize ozone induced changes in inflammatory cytokines in nasal epithelial cell (NEC) biopsy and nasal epithelial lining fluid ELF

The analysis plan is the same as in Aim 1.

Aim 3. Characterize ozone induced changes in FMD, HRV, LVS, Brachial artery ultrasound, ambulatory ECG measures, & other cardiovascular measures.

The analysis plan is the same as in Aim 1.

Aim 4. Characterize ozone induced changes in spirometric measures

The analysis plan is the same as in Aim 1.

Aim 5. Investigate the performance of a wearable monitor for ambient ozone measurement.

There are 2 current devices which will be used (descriptions and photos attached. The subject may wear one or both of these devices. The purpose of these devices at this time is strictly to assess the measured values obtained by the devices compared to the known O3 atmosphere. However, as these devices are prototypes there are two important questions. The

first is will the sensors technically perform appropriately thought the exposure while being worn by volunteers. In essence, the goal of this assessment is to simply see fi the devices work at all, and to identify specific technical modifications which may need to be made. The second goal is to determine if the readings of functioning wearable sensors correlate well with the readings of the standard ozone monitors present in the exposure chamber (that is to demonstrate that they are accurate). All of the ozone sensors are non-invasive. **These are exploratory endpoints**

In case of potential missing data, we will first carefully investigate the pattern of missing data and determine if it is informative missing. In case the missing is heavy, we will explore statistical methods such as multiple imputation to handle the missing data issue (Little and Rubin, 2014).

The pilot design and sample size is motivated by our earlier similar study (Peden et al, 1995). The goal of this pilot study is to determine whether low-level ozone affects a) nasal epithelial inflammation, and b) exploratory cardiovascular endpoints such as heart rate variability. If we find that cardiovascular endpoints are affected by low-level ozone in this small group, further studies will explore these, and perhaps other, cardiovascular markers and outcomes. The aim of these future studies will be to further characterize the cardiovascular effects of low-level ozone exposure.

The sample size for this study is determined on our primary endpoint outlined in Aim 1. The other aims are all secondary analysis using the same sample collected in Aim 1. We will not collect additional subjects for Aims 2-5. In previous literature, it is found that higher-level shorter duration ozone exposure caused a change in neutrophilia of 67 with a standard deviation of 31, while the change is 31 with a standard deviation of 17 in the clean-air group (Peden et al, 1995). The aimed effect size is 36. If we assume the significance level is at 0.05, a sample size of 13 subjects is adequate to ensure 90% power of detecting the effect. Approximately half of the subjects will receive air-ozone sequence, and another half will receive ozone-air sequence. Using a significance level of 0.05, the table below shows the sample size under various potential correlation coefficient. The calculation is based on a two-sided paired t test.

Effect size	Correlation coefficient	Power	N
36	0	0.8	10
	0	0.9	13
	0.3	0.8	8
	0.3	0.9	10
	0.5	0.8	7
	0.5	0.9	9

Note: N means that N/2 subjects receive ozone-air sequence, and another N/2 subjects receive air-ozone sequence.

We anticipate the SD for the proposed study should behave similarly to the previous study. Nevertheless, we inflated our sample size to account for the situation that the true SD is larger than we assumed - our proposed sample size  $n=15$  is larger than the real sample sizes for achieving 80% power, which is  $n=8$  for correlation coefficient 0.3, and  $n=10$  for corr. coeff at 0, respectively.

The statistical analyses will be conducted under the supervision of [name] (Professor of Biostatistics and Director of the CEMALB Biostatistics Core).

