## **2 OBJECTIVES**

### **2.1 Study Outcome Measures**

#### **2.1.1 Primary**

The primary endpoint is the change in nasal PMN counts, measured in nasal lavage fluid, between FA and O3.

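### Section 7 names two-sample tests of air against ozone in a crossover and no primary within-subject analysis, although the sample size assumes a paired t test

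*Combined protocol and SAP*

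**What the plan says.** Section 2.1.1 defines the endpoint as a contrast between the two atmospheres: "The primary endpoint is the change in nasal PMN counts, measured in nasal lavage fluid, between FA and O3". Section 4 has every subject go through both exposures: "The sessions will be identical except for the atmosphere in the chamber, which is randomized".

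Section 7, Aim 1, lists the analyses in this order:

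- a descriptive look at exposure and period effects;
- "two sample tests such as t-test and Mann Whitney test will be used to compare changes in response in clean air and ozone exposure groups";
- a carry-over test, after which "In the absence of significant carry-over effect, pooled data from both periods can be used to estimate the ozone exposure effect", and then "Otherwise, only period 1 data can be used";
- "Finally, a random effects model will be fitted to assess the ozone exposure effect".

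Effect estimates and confidence intervals are promised, but none of these analyses is called primary and the model's terms are not given. For each of Aims 2 to 4 the text is "The analysis plan is the same as in Aim 1". The sample size part of the same section states: "The calculation is based on a two-sided paired t test".

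**The concern.** In a two-period crossover the independent groups are the two sequences. The air and ozone values come from the same people. A two-sample test is sound here in two forms: comparing within-subject period differences between sequences, which uses the pairing, or comparing atmospheres in period 1 alone, which has no pairs. Section 7 states neither. It speaks of exposure groups, and its next step allows both periods to be pooled.

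The reader therefore cannot tell whether the interval reported for the primary endpoint will use the pairing on which the sample size depends. If the correlation within subjects is positive, an analysis that ignores it gives intervals that are too wide. It also loses power for effects smaller than the planned 36. Such effects are plausible, because Section 7 takes 36 from a study with a higher level of ozone.

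**Working it through.** **Inputs (Section 7, sample size).** SD of the change 31 under ozone and 17 under air; effect 67 − 31 = 36; two-sided 0.05; n = 15, taken as sequences of 7 and 8. The documents table correlations of 0, 0.3 and 0.5 but do not estimate the correlation, so all three are shown. Data are taken as normal with no period effect.

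**Step 1: the plan's own table.** SD of the within-subject difference = √(31² + 17² − 2ρ·31·17) = √(1250 − 1054ρ) = 35.36, 30.56 and 26.89. Power of the paired t test comes from the noncentral t with N − 1 df and noncentrality 36√N / SD.

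| ρ | N for 80%: power | N for 90%: power |
|---|---|---|
| 0 | 10: 81.7% | 13: 92.0% |
| 0.3 | 8: 81.4% | 10: 91.1% |
| 0.5 | 7: 83.7% | 9: 93.8% |

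All six tabled sizes are reproduced. The sample size is right for a paired test.

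**Step 2: standard errors at n = 15.**

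- Unpaired: √((961 + 289)/15) = 9.13 at every ρ.
- Paired: SD/√15 = 9.13, 7.89 and 6.94. The unpaired-to-paired ratio is 1.000, 1.157 and 1.315.
- Sequence-group t test on period differences: (SD/2)·√(1/7 + 1/8) = 9.15, 7.91 and 6.96, with 13 df.

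**Step 3: consequences if the two-sample t test (28 df) is run on the pooled data.** Unpaired results are simulated. Power for the paired (14 df) and sequence-group tests is from the noncentral t.

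| | ρ = 0 | ρ = 0.3 | ρ = 0.5 |
|---|---|---|---|
| Type I error, unpaired | 5.3% | 2.7% | 1.4% |
| Mean 95% CI width, unpaired | 37.0 | 37.0 | 36.9 |
| Mean 95% CI width, paired | 38.5 | 33.2 | 29.3 |
| Power for 36, unpaired | 96.7% | 98.1% | 99.0% |
| Power for 36, paired | 95.6% | 98.8% | 99.8% |
| Power for 36, sequence-group | 95.3% | 98.7% | 99.7% |
| Power for 18, unpaired | 48% | 48% | 48% |
| Power for 18, sequence-group | 45% | 56% | 67% |

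Width ratios, unpaired to paired: 37.0/38.5 = 0.96, 37.0/33.2 = 1.11, 36.9/29.3 = 1.26. The effect of 18 is an assumption (half of 36), not a figure from the documents.

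**Step 4: period 1 alone.** With 8 against 7 subjects and a pooled SD of √(1250/2) = 25, SE = 25·√(1/8 + 1/7) = 12.94 and 36/12.94 = 2.78 on 13 df. Power is about 73%. Simulation with the unequal SDs gives 72% to 74%, depending on which atmosphere has 8 subjects.

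**The case against.** The strongest reply is that Section 7 already leans towards a crossover analysis. It plans a carry-over test, pooling across periods and an estimate of the period effect, and two-sample tests between sequence groups are a standard way to do that. It also plans a random effects model with confidence intervals, and subject is the natural random effect, so a paired interval may well be reported anyway. The trial is a pilot, and for the planned effect the paired gain is under one percentage point.

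Much of this stands and lowers the weight of the point. It does not remove it. The text says exposure groups, not sequences. The model has no stated terms, and nothing says which result counts. Pilot or not, the plan claims 90% power for a significance test on this endpoint.

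Three stronger readings are tempting, and the documents do not support them:

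- **No within-subject analysis is planned.** The random effects model can be one; what is missing is its specification and its primary status.
- **False positives are inflated, or the sample size is wrong.** With positive correlation the unpaired test is conservative, at zero correlation it is close to nominal, and the sample size table reproduces.
- **The trial is underpowered for 36 because of the unpaired tests.** Power is about 95% or more in any pooled analysis. The 72% to 74% figure belongs to the period 1 fallback, a separate branch of the plan.

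**Conclusion.** The point holds as a gap between the sample size basis and the analysis text. The named two-sample tests ignore the pairing as worded, and the one planned method that could use it is neither specified nor primary. The text is ambiguous rather than certain to produce an unpaired result.

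If the unpaired t test is run on the pooled data, the 95% interval is 11% wider at a correlation of 0.3 and 26% wider at 0.5. Power for an assumed effect of 18 is 48%, against 56% and 67% for the sequence-group test. At zero correlation there is no loss, and the unpaired interval is about 4% narrower.

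These sizes rest on normal data, the SDs taken over from the cited study, complete data on 15 subjects, and correlations that the documents table but do not estimate. Aims 2 to 4 inherit the wording but carry no power claim. It should be fixed, mainly because the correction is cheap.

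**What to change.** In Section 7, state that when both periods are analysed the primary analysis is a linear mixed model with exposure and period as fixed effects and subject as random effect. Fit it to one response per subject per period: the change in nasal lavage PMN count at a single named post-exposure time. The time must be named because Section 4 collects lavage at baseline, after exposure and 24 hours later.

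With complete data and a subject variance not truncated at zero, this model equals the sequence-group t test on within-subject period differences (13 df at n = 15). Report its estimate and 95% CI. Make paired t or Wilcoxon signed-rank tests supportive. Keep two-sample tests of air against ozone only where period 1 alone is analysed. Apply the same to Aims 2 to 4, each with its own named response.

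The change is wording only: no new data, visits or subjects. The statistical cost is a small loss of power if the correlation is near 0: 95.3% against 96.7% for 36, and 44.5% against 48.0% for 18. The change does not settle whether a carry-over test should choose between the pooled and period 1 analyses; that choice remains in the plan.

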10. Perform nasal epithelial cell biopsy for baseline: a non-invasive biopsy procedure will be performed to retrieve a small cluster of cells from each of the nasal cavities. For the biopsy procedure, the subject will be seated comfortably in a straight-backed chair or reclining on an exam table with the head tilted as far back as possible while remaining comfortable. A short, sterile plastic sampling device called a curette will be inserted into one of the nasal cavities and the surface of the nasal cavity will be stroked several times for approximately 5 seconds in order to obtain a small cluster of cells. Only one side will be collected at this visit. The investigator, study physicians or other trained staff will collect these samples.
11. Introduce the subject to the chamber area by walking them through.
12. Subjects will be discharged with contact information for a study physician on call.

13. **Psychological surveys:** Once subjects have been qualified, they will be emailed a link to complete psychological surveys. These will be performed at home, and at the convenience of the subject, prior to the first exposure session.

Once the subject is deemed eligible, they will return for a baseline day to collect pre-exposure measurements. This visit must occur no less than 3 days and no more than 6 weeks after the screening visit. Subjects will be asked to withhold NSAIDs and antioxidant vitamins for 7 days prior, and to arrive fasting (water is acceptable). We will update any changes in medical history, including medication use, collect vital signs, and perform spirometry.

The following samples will be collected:

1. **Urine pregnancy test:** For all women, if more than 7 days have passed since the prior test.
2. **Epithelial lining fluid (ELF) collection.** This is done by having the subject spray normal saline into the nose, and then insert a small filter paper into each nostril. Nose clips are applied for 2 minutes, then the filter paper is removed. These samples are collected by study staff.
3. **Nasal lavage (NL):** This is done by repetitive spraying of sterile normal saline irrigation solution into the nostril, followed by voluntary expelling of the fluid by the subject into a specimen collection cup. Both nostrils are sampled, these samples will be collected by study staff,

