4. **Spirometry:** Standard spirometry to obtain FEV1 and FVC measurements will be done prior to sputum induction. This is done by having the subject exhale forcefully and completely into a mouth piece attached to a pneumotach. This will be repeated several times, and the procedure will be done following ATS/ERS standards.
5. **Flow-mediated brachial artery dilation (FMD):** This measurement is made by imaging the brachial artery with an ultrasound device. The blood flow to the artery is occluded for 5 minutes, and the artery is again imaged when blood flow is resumed.
6. **Left ventricular strain:** Left ventricular contractility will be assessed by measuring global longitudinal strain using 2-dimensional speckle tracking echocardiography. Apical 4-chamber, 2-chamber, and long axis 2-dimensional ultrasound images of the heart will be acquired using a Philips EPIQ 7 ultrasound machine and stored for subsequent off-line analysis. Global longitudinal strain will be quantified using Philips QLAB advanced quantification software.

The subject will be discharged to home with contact information for a study physician who is on-call if the subject has any health concerns. The subject will return the next morning, and after health history is updated and vital signs collected, the following will take place:

1. **Heart rate variability (HRV):** Standard ECG leads will be placed on the subject's chest, and connected to a monitor that records the heart rate and rhythm. The subject will be asked to lie supine in a quiet, darkened room for up to 30 minutes. The subject will do this before the exposure and immediately after the exposure. The analysis for this measurement is computer based.
2. **Spirometry:** Standard spirometry will be measured prior to the subject entering the exposure chamber.
3. **Ozone monitor:** Subjects will wear an experimental ozone monitor, which is on a bracelet. This is to validate the wearable monitor in an environment with known ozone concentration.
4. **Telemetry:** Standard 3 lead ECG monitoring will be done while the subject is in the exposure chamber.
5. **Symptom questionnaire:** Subjects will be asked to complete a symptom questionnaire prior to entering the chamber.
  

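### Aim 1 appears to compare change-from-baseline scores; prespecifying each session's baseline as a covariate would probably narrow the ozone-air interval, but not if baseline and post-exposure differences are strongly correlated

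*Combined protocol and SAP*

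**What the plan says.** Section 2.1.1 states: "The primary endpoint is the change in nasal PMN counts, measured in nasal lavage fluid, between FA and O3". It does not mention a baseline.

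Section 7, Aim 1, says that two-sample tests (t-test, Mann-Whitney) "will be used to compare changes in response in clean air and ozone exposure groups". It then adds: "Finally, a random effects model will be fitted to assess the ozone exposure effect". The response and fixed effects of that model are not given, and no covariate is named anywhere. For each of Aims 2, 3 and 4 the text is "The analysis plan is the same as in Aim 1".

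The sample-size text in Section 7 uses a mean change of 67 (SD 31) under ozone, and says that "the change is 31 with a standard deviation of 17 in the clean-air group".

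Section 4 gives the sampling. Once eligible, "they will return for a baseline day to collect pre-exposure measurements"; these include ELF, nasal lavage, spirometry, FMD and LV strain, with the subject fasting. For the exposure, "The subject will return the next morning". Lavage is repeated on leaving the chamber after 6.5 hours, with lunch provided inside, and again at 24 hours. The Schematic of Study Design repeats the baseline visit in the second session, so each exposure has its own baseline lavage. The schematic also allows up to two weeks between baseline visit and exposure visit, which does not agree with Section 4.

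**The concern.** In a crossover each subject is their own control, so a stable individual level cancels when the two sessions are compared. Subtracting a session baseline as well helps only as far as that baseline predicts the same session's post-exposure value beyond the subject's usual level. If it predicts little, the subtraction mainly adds measurement noise from two further lavages. Here the baseline is a fasting sample from an earlier day, so a low or moderate correlation is plausible, although the documents give no value.

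A change score fixes the baseline slope at 1, whereas a covariate lets the data estimate it. At stake is the width of the interval for the primary endpoint, and for the Aim 2-4 endpoints that have a session-specific baseline. The plan promises confidence intervals, and Section 7 says the findings will guide further studies, so precision matters.

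**Working it through.** **Plan's own figure.** Section 7 uses effect 36 (67 - 31), SDs 31 and 17, two-sided alpha 0.05 and a paired t test. The SD of the paired difference is sqrt(31² + 17² - 2ρ·31·17), where ρ is the correlation between a subject's two changes: 35.36, 30.56 and 26.89 at ρ = 0, 0.3 and 0.5. The exact (noncentral t) calculation gives N = 10/13, 8/10 and 7/9 for 80%/90% power. All six table entries reproduce. At n = 15 and ρ = 0, power is 95.6%.

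**Comparison of analyses.** For each subject let D be the ozone-minus-air difference in post-exposure values, B the same difference in session baselines, r = corr(D, B), and V = Var(D)/Var(B). This r is not the plan's ρ. Both analyses include a period term, with sequences split 7/8 (assumed).

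- Change score: variance proportional to V + 1 - 2r·sqrt(V), 13 df.
- B as covariate: variance proportional to V(1 - r²), 12 df, with a penalty of about 1 + 1/11 = 12/11 for estimating the slope.
- Width ratio (covariate/change) = k·sqrt[V(1 - r²) / (V + 1 - 2r·sqrt(V))], where k = (2.1788/2.1604)·sqrt(12/11) = 1.053.

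With V = 1 the root simplifies to sqrt((1 + r)/2). The simulated column is the ratio of mean interval widths over 8,000 trials per setting.

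| V | r | Formula | Simulated |
|---|---|---|---|
| 1 | 0 | 0.745 | 0.743 |
| 1 | 0.3 | 0.849 | 0.844 |
| 1 | 0.5 | 0.912 | 0.910 |
| 1 | 0.7 | 0.971 | 0.969 |
| 1 | 0.8 | 0.999 | 0.994 |
| 1 | 0.9 | 1.027 | 1.024 |
| 2 | 0 | 0.860 | 0.857 |
| 2 | 0.3 | 0.969 | 0.963 |
| 2 | 0.5 | 1.024 | 1.024 |
| 2 | 0.7 | 1.053 | 1.049 |

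**In the plan's units (not stated there), V = 1, ρ = 0.** The change-score half-width is 2.1604 × 35.36 × sqrt((1/7 + 1/8)/4) = 2.1604 × 35.36 × 0.2588 = 19.8. Multiplying by the formula ratios gives 14.7 (r = 0), 16.8 (0.3), 18.0 (0.5), 19.2 (0.7), 19.8 (0.8) and 20.3 (0.9).

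**Break-even and worst case.** The widths are equal at r of about 0.80 when V = 1 and about 0.40 when V = 2. The worst case is a true slope r·sqrt(V) of 1, where the change score is already optimal. The variance is then 12/11 = 1.09 times as large and the interval 1.053 times as wide.

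**Against ignoring the baseline.** The change score is noisier than the post-exposure difference alone when 1 - 2r·sqrt(V) > 0, that is, when the slope is below 0.5: r below 0.5 at V = 1, below about 0.35 at V = 2.

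**The case against.** The strongest objection is that the gain depends on two quantities the documents do not give. The plan's own figures also hint that the variances may be unequal: the SD of change is 31 under ozone and 17 under air, as would happen if individual responses to ozone vary and inflate D but not B. At V = 2 the covariate analysis already loses slightly at r = 0.5. Even at V = 1 and r = 0.5, its interval is the narrower one in only about 70% of single simulated trials. This stands, and it rules out any claim that adjustment always narrows the interval.

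Second, the change score is an inference. Section 2.1.1 could mean a post-exposure contrast between atmospheres, and the random effects model might include baseline. In part this stands. But the sample-size text reports a change within clean air alone, which cannot be an ozone-minus-air difference, so change from baseline is the natural reading. A covariate that might be added later is not prespecified.

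Third, a reader might infer that the trial is underpowered or the sample size wrong. The documents do not support that: the table reproduces, and power at effect 36 is already 95.6%. Nor is the change score invalid; the issue is precision.

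Fourth, a reader might apply the point to everything in Aims 2-4. It does not reach NEC, whose only pre-exposure sample is at screening.

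**Conclusion.** The point holds as a cheap, conditional improvement in precision. On the natural reading of Section 7, the plan analyses change scores and names no baseline covariate, although session-specific baselines are collected.

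With n = 15 and equal variances, the expected interval is about 26% narrower at r = 0, 15% at 0.3, 9% at 0.5 and 3% at 0.7, about equal at 0.8, and 2 to 3% wider at 0.9. If the variance of the post-exposure difference is twice that of the baseline difference, it is about 14% narrower at r = 0, 3 to 4% narrower at 0.3, 2% wider at 0.5 and 5% wider at 0.7. The possible gain is thus several times the possible loss.

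These figures assume a within-subject analysis with a period term, a 7/8 sequence split and approximately normal differences; r and V are unknown and shown as a range.

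**What to change.** In Section 7, Aim 1:

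- Define the response as post-exposure PMN, naming which of the two post-exposure lavages is primary.
- Regress each subject's ozone-minus-air difference in that response on the same subject's ozone-minus-air difference in session baseline PMN, with a period term. With the baseline difference left uncentred, the intercept is the ozone effect.
- Keep the change score as a sensitivity analysis.

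Use the same model for ELF, FMD and LV strain. For spirometry and HRV, use the exposure-morning value as baseline. State that NEC is excluded because it has no session-specific baseline.

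Reconcile the baseline timing between Section 4 and the Schematic of Study Design. A longer gap would tend to lower r, which favours the covariate.

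The change needs only plan wording, fixed before unblinding, and no new data. It costs one degree of freedom and, at worst, an interval about 5% wider (about 9% in variance). The sample size does not change.
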